## 2 Background

The theoretical foundations behind early mobility draws its roots from empirical research in the 1950s where the interplay between physiology and psychology was investigated. A line of seminal works showed the cognitive processes that are 'born' and nurtured when toddlers begin to be mobile. The implications of immobility or inefficient mobility in toddlers with physical disabilities were particularly drawn to attention by Butler and colleagues in the 1980s when modified power wheelchairs (PWC) were trialed on toddlers. Early trials focused on testing whether toddlers can learn to use PMT, but as it became established that toddlers can indeed learn to use them, trials moved to measure changes in the child's overall development, particularly their cognitive functioning and social skills.

Over the past 30 years, the negative impact of immobility or inefficient mobility in toddlers with physical impairments has been cast under the spotlight. For typically developing toddlers, the onset of self-produced locomotion has been recognized to induce positive changes in their developmental processes (Campos et al., 2000). Toddlers are observed to learn key skills through mobile play and exploration, but in the presence of physical impairment, the same need for learning these skills through mobility may be hindered. Conversely, children with physical limitations could instead be prone to a condition termed as 'learned helplessness', (Everland, 1984) where they learn, instead, to be resigned to accept their environment and to no longer seek to influence it.

"Children's mastery of functional mobility skills has been classified and categorized in several ways. Hays (1987) examined current existing diagnostic conditions of children without locomotion and divided them into four functional groups" (Wright-Ott, 2015, p.564).

1. *Children who will never ambulate.*

This category includes children with cerebral palsy with severe involvement and spinal muscular atrophy types I and II. Generally, these children have no opportunity for independent mobility.

2. *Children with inefficient mobility who ambulate but are unable to do so at a reasonable rate of speed or with acceptable endurance.*

This category includes children with cerebral palsy with less involvement and myelomeningocele with upper extremity involvement. For these children, assisted mobility may provide an efficient means of mobility above that which they are capable of producing themselves. Warren (1990) uses the term "marginal ambulator" for this group.

3. *Children who have lost their independent mobility.*

This category includes victims of trauma and children with progressive neuromuscular disorders. The developmental implications may be less critical than in the first two groups, and the issue is acceptance of assisted mobility as an adaptation to an acquired disability,

4. *Children who temporarily require assisted mobility and often progress to independent mobility with age.*

This category includes many children with osteogenesis imperfecta and arthrogryposis. Functional considerations in this group are both developmental and practical.

Children with mobility impairments, as categorized by Hays (1987) may benefit from the use of a power mobility device for functional mobility (Wright-Ott, 2015, p. 564) Regardless of the etiology, pathology or prognosis of the condition that limits mobility, children may be able to achieve increased functional mobility, even independent mobility if consideration to other factors are taken into account. These factors include but are not limited to "purpose and goals for the use of the device, environments for intended use, child's physical and psychosocial

abilities and limitations, modifications that may be needed for comfort and control, and cost-benefit ratio" (Wright-Ott, 2015, p. 564).

There are significant differences among these groups that may have implications for mobility and its integration into the child's overall concept of disability, as well as for evaluation and intervention. Group I children may achieve independent mobility through the use of a support walker or power wheelchair. Group II children may be able to independently propel a manual wheelchair, ambulate in a support walker indoors, and use a power wheelchair for community mobility. Children in group III and IV will use a variety of mobility methods during the transition period. (Wright-Ott, 2015, p.564).

"Introduction of Power Mobility Devices (PMD) for some therapists focuses on arbitrary age-based criteria while others look to a set of similarly arbitrary skills that indicate readiness. Researchers have been exploring how young children can begin using PMD. Typically developing infants aged between 5 and 10 months have been successful using a PMD that utilized whole body movement rather than a joystick (Larin, Dennis, & Stansfield, 2012). Researchers at University of Delaware have had success with infants with and without disabilities initiating movement using joysticks at 7 months (Lynch et al., 2009), 11months (Ragonesi & Galloway, 2012) and 14 months-of-age (Galloway et al., 2008). Case studies describe children with age-appropriate cognitive skills using PMD competently as young as 17 months (Zazula & Foulds, 1983), 20 months (Jones, McEwen, & Hansen, 2003), and 22 months-of-age (Everard, 1984). Jones et al (2012) showed that 14-30-month olds who had frequent access to a PMD in the home setting learned successful mobility skills in the presence of significant disability." (Rosen, Plummer, Sabet, Lange, & Livingstone, 2018, p.4). Many practitioners believe that provision of a PMD should be considered within the first year of life (Wright-Ott, 2015, p.563). However, current research suggests that children as young as 5-7 months of age are successful at operating a PMD. Infants, at six months of age begin to be mobile in their environment. Additionally, at 6 months of age an infant has a strong inner drive to reach to midline and engage in bilateral and unilateral reaching, grasping and manipulating objects (such as a joystick). They display adequate head and trunk extension to support themselves in an upright seated position (Parham & Mailloux, 2015, p. 263). "Growing evidence indicates that these early motor experiences not only inform children about their own actions, but also the action of others" (Woodward, 2009). For an infant unable to be independent in self-initiated mobility, the opportunity to explore their environment by accessing a midline-oriented device provides an inherently motivating means of control.

PMD for young children and toddlers has been evolving to provide an efficient option to assist mobile play and exploration; however, no PMD has been successfully marketed in large volumes before. The testing of the Explorer Mini is an innovative and unique mobility device that is well suited to provide an opportunity to assess an infant's readiness to utilize a supported seat and midline control device to demonstrate self-initiated mobility.

### **3 Purpose and Scope**

The scope of the human factors validation test is to demonstrate that the device can be used safely by the intended users, for its intended use. The preliminary analyses, as described in the human factors validation plan, builds the rationale behind the device related tasks included in the test and it will be performed on a device and accompanied labelling that represent the final design.

The test will be performed in a clinical setting including participating children, their parents/guardians and physiotherapists/occupational therapists (PTs/OTs) at three clinical sites in the United States of America, post evaluation and approval from applicable Internal Institutional Review Board (IRB). A clinical setting, while not fully reflective of a home

environment is the typical testing area for mobility related assessments as trained practitioners (PTs/OTs) have access to a variety of devices, and a means of creating a safe environment specific to the child. The clinic is also the place where the child and parent/guardian in real world situation would be introduced to and trained on a mobility device.

## 4 Sample and recruitment

### 4.1 Eligibility criteria

The test participants represent the two populations of intended users:

Primary users – children with mobility impairments

Secondary users – care-givers (parents/guardians and PTs/OTs)

#### 4.1.1 Inclusion criteria

Primary users:

- Informed consent signed by parents or guardian
- Aged 6-36 months
- Unable to mobilize independently for exploratory play and peer interaction, as categorized by Hays (1987)
- Adequate trunk and head control to remain upright in the device, including regain head control
- Adequate hand/ arm (distal) control to reach for objects in front of them

Evaluation of children has traditionally focused on achievement of developmental milestones. However, underlying impairments cannot fully explain the extent and form of functional difficulties seen in children with mobility impairments (Coster, 1998). Additionally, "the tasks most relevant for functional mobility have not been well defined in traditional developmental milestone test" (Wright-Ott, 2015, p. 564). In this test, all included children have a mobility impairment but for reasons described above, no specific diagnosis is set as inclusion criteria for the primary user and the mobility impairment of the user will depend on a variety of diseases, diagnoses, cognitive or functional disorders.

Secondary users:

- Signed informed consent
- PT/OT or parent/guardian of the child included in the test

#### 4.1.2 Exclusion criteria

Primary users:

- Weight >16 kg/35 lbs
- Length >100 cm/39 in
- Children that lack head control in such a severe manner that they cannot regain control if it is lost
- Children who do not show awareness of or respond to toys, objects, sounds and/or people in their environment
- Any other reason, if in the opinion of the investigator, the individual user is not appropriate, or suitable for participation in the test.

Secondary users:

- Hearing/vision loss or limited cognitive skills impacting the ability to take instructions and perform the tasks of the test
- Ability to understand oral and written English as product labelling will in this HF validation test only be available in English
- Any other reason, if in the opinion of the investigator, the individual user is not appropriate, or suitable for participation in the test

## 4.2 Sampling

Because successful mastery of a power mobility device has been demonstrated with children over the age of 17 months, and children as young as 7 months demonstrate early skills necessary for power mobility the testing groups will be set at 6-17 months and 18-36 months. It is anticipated that children with supported trunk (proximal) control will have adequate hand/arm (distal) control and inherent motivation and development to operate a midline-oriented control.

Enrollment of eligible children will be conducted to ensure 30 per protocol performed tests, 15 children per age group.

6 months – 17 months	15 children
18 months – 36 months	15 children

Along with the 30 children, their 30 parents/guardians will be actively participating in the study as well as their PT/OT.

## 4.3 Recruitment

Recruitment will be initiated after a favourable decision from the local IRB has been received. The study clinics will be participating in this test, recruiting 10 children/parent pairs each. The principal investigators will reach out to PTs/OTs, to identify children managed by them who would match the inclusion/exclusion criteria of this test. A recruitment script may be used (see attachment 4). It is expected that there is an established connection between the child and the PT/OT already prior to this test.

### 4.3.1 Informed consent

Informed consent will be obtained prior to the participants undergoing any activities that are specifically for the scope of the test. In the process of gaining informed consent, the child's parents/guardian and PT/OT will receive information about the nature and objectives of the study, possible risks associated with their participation, their free choice of participating and leaving at any time, both in writing and orally. They will also have the opportunity to ask questions and be able to retain the information long enough to make an effective decision.

## 5 Study design and conduct

This is a descriptive, cross-sectional study to evaluate users' interactions with and perceptions of the device user interface. This will be done in two major steps:

- Observations of users' performance of all critical and some non-critical tasks identified in the preliminary analyses and evaluations (observational data)
- Debriefing interview to collect the users' perspective of the device (interview data)

## 5.1 Methodology

The introduction of the device to the children and caregivers will, once the product is commercially available, be performed by a PT/OT. Supplemental instructions will be given in the user's manual. In order to validate that the device is safe to use also without having received any training, the first observational part of the study will be performed in three steps.

1. To simulate an initial encounter with the device for a PT/OT where the device may be handled without any additional instructions, the child's PT/OT will first perform the test tasks untrained. The PT/OT will be provided with the User's manual but may not be prompted to use it for written information of the product.
2. In standard of care, after having learned how to use the device, a PT/OT would show the parent/guardian how to operate the device. In step two, the Principal Investigator will train the parent/guardian and the PT/OT on the device (standard product training) supported by references to the Users' manual.
3. The parent/guardian performs the test tasks, supported with the Users' manual and PT/OT or Principal Investigator.

The Principal Investigator will provide arm's length supervision throughout all steps of the study to ensure the safety of all participants.

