### 5.1.2 HF Validation test – Observations

1. The child's PT/OT is presented to the device and it's labelling and is asked to:
  - connect the battery charger to the battery charging port, and disconnect it.
  - adjust the seat and table height so that they are appropriate for the child.
  - adjust the speed of the device so that it is appropriate for the child.
  - place the child into the device.
  - if needed, adjust cushion and/or other support to ensure that the child is placed properly and safely.

The PI documents the observations on an observation form, attachment 1.

2. The Principal Investigator presents the device and labelling (including user manual) to the parent/guardian and PT/OT and performs a standard product training of the device.
3. The parent/guardian is presented to the device and it's labelling and is asked to:
  - connect the battery charger to the battery charging port, and release it.
  - adjust the seat and table height so that they are appropriate for the child.
  - adjust the speed of the device so that it is appropriate for the child.
  - place the child into the device.
  - if needed, adjust cushion and/or other support to ensure that the child is placed properly and safely.

The PI documents the observations on another observation form, attachment 1.

The activities above are derived from the risk-analysis of the device, performed prior to this test, and are performed by the secondary users, where the child is needed in order to perform them but does not play an active role.

One PT/OT may be the professional care-giver to more than one of the children included in the test. Step one above will only be performed once for an individual PT/OT.

4. As the child is placed in the device by the parent/guardian, the child is allowed to explore the device for 5 minutes. The child will be instructed to place their hand on the joystick and watch how he/she can move it. If the child does not initiate after a verbal prompt the Principal Investigator will place the child's hand on the joystick. The child test form, attachment 3, will be used to describe the child's actions and reactions.

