If the child seems interested they may be placed in the device up to two times during the visit, with at least five minutes of rest in between. If the child shows signs of distress (such as crying) for at least one-minute, then they will be taken out of the device for a five-minute rest period. A new attempt will be made to place the child in the device. A maximum of three, one-minute attempts will be made to provide an opportunity for the child to use the device before this step is ended.

The Principal Investigator will use the observation form for secondary users to document observed user problems and use errors during the test, see attachment 1.

The Principal Investigator will complete two forms per test:

1. The child's PT/OT (performing the test without training)
2. The child's parent/guardian (performing the test with training)

The Principal Investigator will use a child test form for primary users to document observed user problems and user errors during the test as well as the ability to get the device in motion and the child's actions and reactions.

User errors performed during the tasks will be divided into three severity levels:

1. User experienced difficulties in performing the task but did not lead to harm
2. User performed an error that could have resulted in harm but never did
3. User performed an error that resulted in harm.

Details of the risk analysis performed in the preliminary analysis can be found in the Human Factors validation plan ES1692.

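### The parents' only run may be helped by the PT/OT or investigator with no stated limit, so observed parent use errors may be understated by an unknown amount

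*Protocol*

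**What the plan says.** Section 5.1 of the protocol sets out the observational part in three steps. In step 1 the PT/OT does the tasks untrained, with the manual provided but without being prompted to consult it. In step 2 the investigator trains both the parent/guardian and the PT/OT. Step 3 is the parent's turn: "The parent/guardian performs the test tasks, supported with the Users' manual and PT/OT or Principal Investigator".

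The same section states safety oversight in a separate sentence covering every step: "The Principal Investigator will provide arm's length supervision throughout all steps of the study to ensure the safety of all participants".

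Section 5.1.2, step 3, introduces the parent's task list with "The parent/guardian is presented to the device and it's labelling and is asked to" and says nothing there about support. The investigator documents the observations on a second copy of the observation form (Attachment 1). One form is completed for the parent, in the trained condition.

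The form is used "to document observed user problems and use errors during the test, see attachment 1". Three severity levels follow. Level 1 is "User experienced difficulties in performing the task but did not lead to harm", level 2 is "User performed an error that could have resulted in harm but never did", and level 3 is an error that did cause harm.

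On the PT/OT run, section 5.1.2 adds: "Step one above will only be performed once for an individual PT/OT".

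**The concern.** Sections 3 and 6.1 ask whether the intended users can operate the device safely and without serious use errors, and section 4.1 counts parents/guardians among those users. The information on parents comes from watching them do the tasks. If a trained clinician or the investigator may step in freely during that one run, some errors that would have occurred never appear. The effect runs in one direction: help can remove an error from the record, and is unlikely to add one.

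The people allowed to help are the PT/OT, who has just had the same product training, and the investigator, who gave that training and also fills in the form. Without a rule on when help is allowed and a note of when it was given, a report reader cannot tell a task the parent managed alone from one steered to completion. That distinction is hard to reconstruct after the visit.

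**Working it through.** **Number of parent runs.** Inputs: three sites (section 3), 10 child/parent pairs per site (section 4.3), and 15 children in each of two age groups (section 4.2). 3 × 10 = 30 and 15 + 15 = 30, which agrees with the 30 parents/guardians in section 4.2.

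**Exposure.** Section 5.1.2, step 3, lists five parent tasks; the fifth (cushion or other support) is done only when needed. Parent task runs: 30 × 4 = 120 to 30 × 5 = 150. None is required to be unaided. Help is permitted, not required, so the number helped lies between 0 and all of them. PT/OT step 1 runs number at most 30, fewer where one PT/OT serves several children.

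**Does supported mean only safety oversight?** No. Supervision at arm's length has its own sentence and applies to all steps. Support from a person is named for step 3 alone, so it adds something.

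**Is the help limited?** Step 1 carries a rule against prompting. Step 3 has no counterpart, and neither does the task list in section 5.1.2.

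**What can be recorded?**

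| Event in the parent run | Where it fits |
|---|---|
| Visible difficulty, or a request for help | User problem; level 1 |
| Error made, then caught | Level 2 |
| Error causing harm | Level 3 |
| Error headed off by unsolicited help before any difficulty shows | None of the three levels |

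Level 1 needs a difficulty and levels 2 and 3 need an error that was performed, so the last row is the gap.

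**Illustration only.** The protocol gives no error rate and no share of helped tasks. Suppose a task has true unaided error rate p, help pre-empts a share h of those errors, and the 30 parents are independent. The chance of seeing at least one error is 1 − (1 − p(1 − h))^30:

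| p | h = 0 | h = 25% | h = 50% | h = 75% |
|---|---|---|---|---|
| 5% | 78.5% | 68.2% | 53.2% | 31.4% |
| 10% | 95.8% | 90.4% | 78.5% | 53.2% |
| 20% | 99.9% | 99.2% | 95.8% | 78.5% |

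For example, with p = 10% and h = 50%: 1 − 0.95^30 = 78.5%.

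If no error is seen in 30 runs, the one-sided 95% upper limit is 1 − 0.05^(1/30) = 9.5%. Dividing by (1 − h) to refer it to unaided use gives 12.7%, 19.0% and 38.0% for h = 25%, 50% and 75%. These figures show how the result depends on h. They are not evidence that masking occurs, and h cannot be estimated unless help is recorded.

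**The case against.** The strongest reply is that supported use is the intended use. Section 5.1 describes standard care in which, "after having learned how to use the device, a PT/OT would show the parent/guardian how to operate the device", and section 3 places a parent's introduction to the device in the clinic. Support may also mean only that the manual and the people are at hand. Both points carry weight: having support present is not itself a flaw. But neither limits the help, and section 3 concedes that the clinic does not fully reflect the home. The protocol does not confine its conclusion about parents to supported use.

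A reader might infer more than the document supports, in four ways:

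- That pre-empted errors leave no trace at all. This cannot be shown. Section 5.1.2 has the investigator document observations in general terms, Attachment 1 and ES1692 are not shown, and the interviews in section 5.1.3 may bring some help to light.
- That the untrained PT/OT run is irrelevant because PTs/OTs are a separate population. Section 4.1 puts them with parents in one secondary-user population, doing the same tasks. What remains is that PTs/OTs are professionals, so their run does not show how parents perform.
- That a success rate is inflated. The protocol defines none. The claim can only be about observed use errors and problems.
- That every parent run is assisted. Help is allowed, and its frequency is unknown.

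How helped tasks enter any formal tabulation may properly be left to an analysis plan. Whether help may be given is test conduct, which this protocol fixes.

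**Conclusion.** The point holds in a narrow form. As written, the parents' single run allows personal help without a stated limit, and an error averted by unsolicited help falls outside the three severity levels. Observed parent use errors may therefore be understated. The direction follows from the design; the size cannot be estimated from the protocol. The 120 to 150 parent task runs measure exposure only.

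The conclusion assumes that support in step 3 goes beyond safety supervision, as the separate sentence implies, and that no unseen document limits the help. If Attachment 1 or ES1692 already records help, the recording part is met and only the missing limit remains. This change should be made, with medium confidence; it does not undermine the study as a whole.

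**What to change.** In section 5.1, step 3, and section 5.1.2, step 3, state that after training the parent/guardian first attempts each task with the user's manual, and that the PT/OT or investigator helps only on request or for safety. Leave the arm's-length supervision unchanged.

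For each parent task, record whether it was unaided, helped or intervened on, using Attachment 1 if it does not already have such a field. Describe helped tasks separately in the human factors validation report.

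If supported use is the intended model, keep step 3 as it stands, record help in the same way, and word the conclusion on parents/guardians as applying to supported use.

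The cost is wording in two sections and the report, and at most one form field. No extra staff or participants are needed. Visits may run slightly longer, by an amount the protocol does not let one estimate, and more use errors may be observed. The change has to be in place before testing starts, because unrecorded help cannot be reliably recovered later.
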